#### Anatomic description of lymphatic pathways draining the uterus

**The upper paracervical pathway (UPP)** follows the uterine artery to the pelvic side wall draining primarily to the external iliac and obturator nodal compartments, then running lateral to the common iliac artery further to the paraaortic area.

**The lower paracervical pathway (LPP)** follows the ventral rim of the sacrouterine ligament, primarily to internal iliac and presacral nodes, then running medial of the common iliac artery further to the paraaortic area.

The infundibulopelvic ligament pathway (IPP) runs via the Ip-ligament further to the supramesenteric paraaortic area.

Assuming that lymph runs from the uterus and then cranially, supramesenteric paraaortic true paraaortic SLN's logically can only be defined when inframesenteric lymph are not ICG positive: Theoretically this may occur in situation when no pelvic nodes are dyed or when ICG have dyed pelvic nodes but not have been distributed further to the inframesenteric node, i.e that ICG goes directly to the supramestenteric nodes via the IP-ligament.

Alternatively, when inframesenteric paraaortic nodes are ICG positive via the UPP and /or the LPP but no pelvic nodes in these pathways are dyed.

For the pelvic SLN concept, ideally one SLN should be identified per LPP and UPP per pelvic side wall.

### Anatomic plan for localization of sentinel lymph nodes

Injection site of ICG and Tc99nanocolloid 

Cervix

[figure not shown]
Reinjection ICG cervix:  $\Box$  yes  $\Box$  no

IPligament

Display after first injection

Display after second injection

	UPP	LPP	IP- ligament		UPP	LPP
Right				Right		
Left				Left		

Mark position and type of SLN on anatomical chart with number corresponding to position and number at list and on separate jars for each SLN.

**O** = ICG positive juxtauterine Sentinel node **(SLN1**)

FICG neg juxtauterine lymph node with afferent lympahtic vessel (SLN 2)

X = Tumor suspect lymph nodes regardless of mapping (SLN makro)

#### Sentinel node in cervical cancer

Version 1.2 180914

List of nodal specimens ( swedish) Cervical cancer ICG+TC99 ID date Om preparat saknas från station stryks raden i listan. Burknumrering behålls för övriga prep.

KK	Körtelposition	Patol	Dosa	Antal bitar	Mikro	Varav
Burk		burknr	nr		Antal	med
nr					körtlar	metast
1	Uterus, höger ovarium & tuba,					
2	vänster ovarium & tuba					
3	Höger tuba Vänster tuba					
4	SLN Parametrium höger					
4	SLN Parametrium vänster					
6	Lgl Externa höger ICG NEG Techn NEG					
7	Lgl Externa höger ICG POS Techn NEG					
8	Lgl Externa höger ICG POS Techn POS					
9 10	Lgl Externa höger ICG NEG Techn POS					
10	Lgl Obt. höger ICG NEG Techn NEG Lgl Obt. höger ICG POS Techn NEG					
11	Lgl Obt. Höger ICG POS Techn POS					
12	Lgl Obt. Höger ICG NEG Techn POS					
13	Lgl Comm höger ICG NEG Techn NEG					
14	Lgl Comm höger ICG POS Techn NEG					
15	Lgl Comm höger ICG POS Techn POS					
10	Lgl Comm höger ICG NEG Techn POS					
17	Lgl Presacralt hö ICG NEG Techn NEG					
10	Lgl Presacrait hö ICG POS Techn NEG					
20	Lgl Presacrait hö ICG POS Techn POS					
20	Lgl Presacrait hö ICG NEG Techn POS					
21	Lgl Externa vällCG NEG Techn NEG					
22	Lgl Externa vä ICG POS Techn NEG					
23	Lgl Externa vä ICG POS Techn POS					
24	Lgl Externa vä ICG NEG Techn POS					
25	Lgl Obt. vänster ICG NEG Techn NEG					
20	Lgl Obt. vänster ICG POS Techn NEG					
28	Lgl Obt. vänster ICG POS Techn POS					
20	Lgl Obt. vänster ICG NEG Techn POS					
30	Lgl Comm vänster ICG NEG Techn NEG					
31	Lgl Comm vänster ICG POS Techn NEG					
32	Lgl Comm vänster ICG POS Techn POS					
33	Lgl Comm vänster ICG NEG Techn POS					
34	Lgl Presacralt vä ICG NEG Techn NEG					
54			1			

#### Sentinel node in cervical cancer

Version 1.2 180914 Lgl Presacralt vä ICG POS Techn NEG 35 36 Lgl Presacralt vä ICG POS Techn POS 37 Lgl Presacralt vä ICG NEG Techn POS 38 Lgl Ned aortabif ICG NEG TECHN NEG Lgl Ned aortabif ICG POS TECHN NEG 39 Lgl Ned aortabif ICG POS TECHN POS 40 Lgl Ned aortabif ICG NEG TECHN POS 41 42 Lgl Paraaortal nedom IMA ICG NEG Techn NEG Lgl Paraaortal nedom IMA 43 ICG POS Techn NEG Lgl Paraaortal nedom IMA 44 ICG POS Techn POS Lgl Paraaortal nedom IMA 45 ICG NEG Techn POS 46 SLN typ 1 ICG POS Techn Neg SLN typ 1 ICG POS Techn Neg 47 SLN typ 1 ICG POS Techn Neg 48 SLN typ 1 ICG POS Techn POS 49 SLN typ 1 ICG POS Techn POS 50 SLN typ 1 ICG POS Techn POS 51 SLN typ 2 ICG NEG Techn NEG 52 53 SLN typ 2 ICG NEG Techn NEG SLN typ 2 ICG NEG Techn POS 54 SLN Makro ICG pos radio pos 55 ICG neg radio neg SLN Makro ICG pos radio pos 56 ICG neg radio neg 57

SLN anges i fritext i tabell och med tryck RÖD klisteretikett på burk. Vid behov av sep histologi (tex bulky nodes) används fritext i tabell och numrering 50 ff samt etikett+ fritext på burk avseende lokal / orsak

Sentinel node definieras som den mest uterusnära ICG pos körteln i respektive kompartment där man identifierar en separat afferent lymfbana

KK Burk	Körtelposition	Patol burk	Dosa nr	Antal bitar	Mikro Antal kärtlar	Varav med
nr 1	Uterus, höger ovarium & tuba,	nr			körtlar	metast
1	vänster ovarium & tuba					
2	Lgl Iliaca Externa höger ICG NEG					
3	Lgl Iliaca Externa höger ICG POS					
4	Lgl Obturatorius höger ICG NEG					
5	Lgl Obturatorius höger ICG POS					
6	Lgl Iliaca Communis höger ICG NEG					
7	Lgl Iliaca Communis höger ICG POS					
8	Lgl Presacralt höger ICG NEG					
9	Lgl Presacralt höger ICG POS					
10	Lgl Iliaca Externa vänster ICG NEG					
11	Lgl Iliaca Externa vänster ICG POS					
12	Lgl Obturatorius vänster ICG NEG					
13	Lgl Obturatorius vänster ICG POS					
14	Lgl Iliaca Communis vänster ICG NEG					
15	Lgl Iliaca Communis vänster ICG POS					
16	Lgl Presacralt vänster ICG NEG					
17	Lgl Presacralt vänster ICG POS					
18	Lgl Paraaortalt nedom IMA ICG NEG					
19	Lgl Paraaortal nedom IMA ICG POS					
20	Lgl Paraaortal ovan IMA ICG NEG					
21	Lgl Paraaortalt ovan IMA ICG POS					
22	SLN Parametrium höger					
23	SLN Parametrium vänster					
24	SLN typ 1 presacralt höger					
25	SLN typ 1 presacralt vänster					
26	SLN typ 1 iliaca externa höger					
27	SLN typ 1 obturatorius höger					
28	SLN typ 1 iliaca externa vänster					
29	SLN typ 1 iliaca obturatorius vänster					
30	SLN typ 1					
31	SLN typ 1					

## List of nodal specimens (Swedish) cervical cancer Tracer ICG pat-id date

## Sentinel node in cervical cancer

version	/0151011 1.2 180914					
32	SLN typ 2					
33	SLN makro ICG pos					
	ICG neg					
34	SLN makro ICG pos					
	ICG neg					
35						

om preparat saknas från station stryks raden i listan. Burknumrering behålls för övriga prep.

Numbers 30-34 will be used for describing locations outside the most common sites and for SLN type 2 and SLN macro as appropriate. The locations will be written by hand on list and labels for jars.

#### Histopathologic evaluation of the sentinel nodes and the non-sentinel nodes.

At final pathological examination, all macroscopically identified SLN lymphoid tissue will be embedded and bisected at the minimum thickness exceeded 3 mm. Ultrastaging using hematoxylin/ Eosin staining will be performed in five sections at three different levels , separated by 200 µm. First and second level immunohistochemistry (pan-cytokeratin, MNF 116) will be performed if the maximum diameter of the SLN tissue exceeds one mm. If no macroscopically lymphoid tissue is identified in SLN or parametrial tissue the most suspicious find will be embedded and microscopically investigated. ITC can be detected by Hematoxylin/Eosin or by Immunohistochemistry alone.

Non- SLN nodes less than 3 mm in thickness will be embedded whole, and from nodes thicker than 3 mm at least half the node will be embedded. The slides will be evaluated after hematoxylin/Eosin staining.

#### Classification of tumor size in SLN's

Sentinel nodes will be classified according to a modification of the AJCC staging for axillary nodes from breast cancer as follows:

Macrometastases = tumor greater than 2.0 mm in diameter.

Micrometastases = tumor cell aggregates between 0.2 and 2.0 mm in diameter.

Isolated tumor cells =individual tumor cells or aggregates that are less than 0.2mm in

diameter, usually detected by immunohistochemistry.

Tumor absent – no tumor cells identified in H&E (or immunohistochemically, if applicable) stained sections.

Non-sentinel lymph nodes will be reported as positive or negative for metastases based upon routine sectioning and examination of a single H&E stained section.

#### Sentinel node in cervical cancer Version 1.2 180914 5.0 TREATMENT PLAN

-Intraoperative cervical injection of Tc 99 nanocolloid and ICG (immediately before onset of surgery)

-Intraoperative lymphatic mapping and sentinel node identification with robotic NIR/fluorescence imager and gamma probe will be used for an initial transperitoneal, then retroperitoneal evaluation of display of ICG fluorescence/ radiopositivity. The retroperitoneal dissection with opening of the avascular planes saving the lymphatic vessels will start presacrally then further with the pelvic side walls. The upper lymphovascular parametria will be kept intact by a careful opening of the pararectal and paraveiscal spaces. -An ipsilateral reinjection of ICG will be performed in case of non-display of either of UPP or LPP. If the sentinel node cannot be identified in a particular pathway following a 15-20 minute search, the case should be described as a ICG-negative mapping event for that pathway. A initial scanning of the pelvic side walls and presacral area will be performed - A reinjection of ICG will be performed in case of non-display of the UPP and LPP bilaterally.

-The results of the lymphatic mapping will be marked on the anatomic plan and the specimens and labeling of those will be according to descriptions above.

-The complete SLN algorithm should be adhered to, i.e in case of a ICG negative mapping (for **SLN type 1 and 2, ICG defined**) and / or radio negative mapping any macroscopically metastase suspect nodes should be removed and defined as **SLN macro**. All patients will be subject for at least a full pelvic lymphadenectomy after removal of SLN.

-The upper lymphocascular parametrial tissue (the tissue medial of the obliterated umbilical artery, with the supravesical artery as distal/ventral border, the ureter as dorsal border and including tissue adjacent to the inner side of the broad ligament) will be removed and evaluated the same way as SLN's. This is to investigate the presence of lymph node in the upper parametria, theoretically the most juxtauterine nodes, hence the SLN.

-All SLN and the upper parametrial tissue will be subject for later ultrasectioning and IHC Histopathologic evaluation.

 In case of metastatic SLN the lymphadenectomy will be extended to the level of the inferior mesenteric artery and the hysterectomy aborted in favour of radiochemoptherapy. In case of a planned trachelectomy this will be transformed to

a radical hysterectomy.

-A Querleu-Morrow type B2 or C2 hysterectomy or robotic radical trachelectomy will be performed as appropriate or aborted in case of metastatic LSN at surgeons discretion and patients' wish.

- Adnexal surgery or transpositioning of the adnexa shall be performed at surgeons discretion and patient' wish.

- Complications will be recorded and subdivided to enable association with parts of the procedure, most importantly, the SLN procedure as such and the lymphadenectomy. The classification described under the adverse events tables will be used.

NOTE: Surgeon skill and adherence to protocol will be verified as described.

#### 6.0 TREATMENT MODIFICATIONS

In case of no ICG uptake (including reinjection according to protocol) or radiopositivity the overall SLN algorithm should be followed, i.e removal of any macroscopically suspect nodes and as planned a full compartmentwize lymphadenectomy.

In case of conversion to open surgery before identification and removal of SLN's the patients should be included in evaluation of adverse events and feasibility on an intention to treat basis but not included in the calculation of sensitivity and negative predictive values for the sentinel node concept.

In case of metastatic SLN on frozen section, the lymphadenectomy should be extended to the level of the inferior mesenteric artery, a planned trachelectomy converted to a radical hysterectomy and at surgeons discretion and patient wish a planned radical hysterectomy completed or aborted in favour of radiotherapy. Adnexal surgery / transposition of ovaries shall be performed at surgeons' discretion and patient wish.

#### 7.0 STUDY CRITERIA

#### **Observations and Tests**

The following observations and tests are to be performed and, where appropriate, recorded on the designated form(s) (Appendix A):

PARAMETER	Pre-operative	Intraoperative	Postoperative
Log on approached patient	Х		
Log on included patients and	Х		
patients' withdrawal from study			
before surgery			
History & Physical examination	X		
Examination and evaluation by			
surgeon and anesthetist			
Laboratory test	Х		Х
Hb, S-electrolytes, S-kreatinine			
CRP, Trc, coagulation test when			
appropriate			
Injection data for ICG including	X	Х	Х
drug related adverse events			
		X7	
Sentinel nodes identification		Х	
Recording of intraoperative		X	
adverse events			

Sentinel node in cervical cancer Version 1.2 180914		
Histologic evaluation of sentinel		Х
nodes and non-sentinel nodes		
Decending of next on		Х
Recording of post-op		Х
complications until 30 days after		
surgery		
Recording of lymphatic		
complications on validated		
questionnaire at symptoms and at		
one year after surgery		

Adverse Events will be captured from time of ICG administration until30 days after surgery

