#### **1. OBJECTIVES**

To estimate ICG and Radiocolloid alone and in combination to estimate any advantage of the combination of both tracers in terms of technical success rates/ bilateral mapping, sensitivity and false negative rates for the detection of pelvic SLN (first 75 patients).

To estimate the sensitivity and negative predictive value of the pelvic sentinel lymph node (SLN) concept for determination of lymph node metastases in patients with early stage cervical cancer planned for robotic surgery using either a combination of ICG and Radiocolloid or in case ICG alone is equal to or superior (in terms of technical success rate, bilateral mapping rates) to the combination the use of ICG as tracer for cervical injection using an anatomically based surgical algorithm and definition of sentinel lymph nodes.

To estimate if reinjection of tracer (ICG) will enhance the technical success / bilateral mapping rates.

To estimate the proportion of cervical cancer patients suitable for the SLN concept in conjunction with robotic surgery

To estimate complications associated with the detection and removal of SLN as such.

To estimate complications associated with ICG as tracer.

To estimate the incidence of lymphatic complications by the use of a validated questionnaire

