#### 2. BACKGROUND

The surgical approach for cervical cancer staging has changed from conventional laparotomy to a more minimally invasive technique with proven advantages in terms of less perioperative morbidity. Robotic assisted laparoscopic radical hysterectomy with pelvic lymph node dissection has emerged as the approach of choice for an increasing number gyne-oncologists worldwide. Previous data from the department of Obstetrics and Gynecology in Lund, Sweden, shows that robot assisted surgery feasible for 95% of unselected cervical cancer patients selected for primary surgery. In cervical cancer, nodal involvement is a strong prognostic factor and also determines

adjuvant treatment and a pelvic lymphadenecomy is recommended for cervical cancer stages 1a2 and higher stages where primary surgery is recommended. A pelvic lymphadenectomy is associated with an increased risk for lymphatic complications such as lymphedema, lymphocysts and in rare cases lymphatic ascites.

The concept of identifying nodal metastases by detection of sentinel lymph nodes as a marker of nodal metastatic disease or not therefore is appealing. However, during later years many studies have been published, most of the retrospective, using a variety of tracers and with little or no information on used surgical algorithm, used definition of SLN and without reference to lymphatic anatomy. Moreover, technical success rate varies. A high technical success rate is cruzial to avoid the need for a full hemipelvic or pathwaywize LND in case of failure. In pilot studies from Lund University we have shown that reinjection of tracer (ICG) increases the technical success rates both defined per hemipelvis and pathwaywize, defined by detection of at least one SLN per hemipelvis to around 95%. By the use of Indocyanine green, a fluorescent tracer, we have also previously demonstrated two bilateral separate pelvic pathways, the upper paracervical pathway (UPP) running along the upper lymphovascular parametrium usually to external iliac and/ or obturator nodes and the further lateral to the common iliac artery to paraaortic nodes and the lower paracervical pathway (LPP) running via the sacrouterine ligament to nodes medial of the internal iliac artery and/ or presacral nodes then further medial to the common iliac artery to paraaortic nodes. Hence there are two bilateral pelvic pathways draining further to the paraaortic region below as well as above the inferior mesenteric artery.

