#### **Exclusion Criteria**

-Non consenting patients

-Ongoing pregnancy

-Inability to understand written and/or oral study information

-Who performance status III or more

-Previous lower limb lymphedema

-Surgical contraindication to a laparoscopic approach or lymphadenectomy at surgeons discretion.

-Anesthesiologic contraindication to a laparoscopic approach at the anesthetist's discretion

- Locally advanced disease or intraabdominal/distant metastases at preoperative CT, MRI or ultrasonography

- Radiologically suspect pelvic nodal metastatic disease according to the RECIST criteria

 $(\geq 1 \text{ node with} \geq 16 \text{ mm short axis diameter})$ 

-Allergy to Iodine

-Patients with a known liver disease

-Patients with a significant bleeding disorder or mandatory antithrombotic treatment.

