#### 8.0 EVALUATION CRITERIA

-Technical success rates, sensitivity and false negative rates with ICG and Tc99 nanocolloid will be compared per patient, per hemipelvis and per pathway, UPP and LPP.

- All patients who are injected with tracer and not converted to open surgery before detection and removal of SLN's will be included for evaluation of technical success rate (described per patient, per hemipelvis and per separate pathway) after first and in case of non-dispay of any of the LPP and UPP after reinjection of ICG as described.

- Patients with at least one SLN type1-2 identified will be included for determining the sensitivity and the negative predictive value for the SLN ICG concept. In addition the overall SLN concept, including SLN macro will be evaluated as of above.

- All patients included, regardless of conversion to open surgery and mapping of ICG (or the combination of ICG and Tc99 nanocolloid) will be included in the evaluation of feasibility and safety.

- Intraoperative adverse associated with the detection and removal of SLN will be evaluated and reported separately on all patients who have at least one SLN removed regardless of type, i.e all patients in whom SLN were removed separately.

- Postoperative complications until 30 days after surgery will be reported.

-The incidence of lymphatic complications defined by the questionnaire will be evaluated

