For the first stage we estimated a total of 226 patients to be included taking into consideration a 95% bilateral SLN detection rate, and an estimated 15% rate of node positivity including an increase in node positivity rates due to ultrasectioning and immunohistochemistry. For the second stage, another 187 patients have to be included. As the number of node positive patients will be reported continuously to the study coordinator this will be decisive of the number of patients that has to be included for each stage.

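### With no preoperative lymphatic questionnaire, questionnaire-defined incidence may be overstated by leg complaints that were present before surgery

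*Combined protocol and SAP*

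**What the plan says.** The last objective in section 1 is "To estimate the incidence of lymphatic complications by the use of a validated questionnaire". Section 8 makes the instrument the case definition: "The incidence of lymphatic complications defined by the questionnaire will be evaluated".

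The schedule in section 7 (Observations and Tests) names two occasions in the text of the row: "questionnaire at symptoms and at" "one year after surgery". On a natural reading, both follow surgery. The table came through the PDF extraction damaged and this row shows no mark in any column, so nothing is inferred from the columns. The timing rests on the row wording alone.

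Two other provisions bear on status before surgery. Section 3 excludes women with "Previous lower limb lymphedema", and section 7 lists "History & Physical examination" preoperatively without specifying a limb or lymphatic symptom assessment.

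The documents do not name the questionnaire, give a cut-off for a positive result, state a rule for new or worsened complaints, or give an expected rate for this objective.

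**The concern.** Incidence counts new cases among people free of the condition at the start. If the condition is whatever the questionnaire calls positive, the starting status has to be known on that questionnaire. Without it, a woman who had leg swelling or heaviness before surgery for another reason, and still has it at one year, can be counted as a lymphatic complication of the operation.

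Nothing else in the design supplies the missing reference. Every patient is planned for at least a full pelvic lymphadenectomy after the sentinel nodes are removed, so no unoperated group shows the background level of complaints. Section 11 has patients act as their own controls, but only for nodal status. The adverse event definition in section 10 does separate new problems from worsening of existing ones; the questionnaire outcome has no baseline on which to apply that distinction.

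At stake is the figure the trial would report for lymphatic morbidity. A bias of this kind does not shrink as more patients are enrolled, and a preoperative reading cannot be taken after the operation.

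**Working it through.** **Plan's own figure.** None is stated for this objective, so there is nothing to reproduce. The calculation below only shows scale.

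**Inputs.**
- N = 226, from section 11: "For the first stage we estimated a total of 226 patients to be included".
- N = 413 if the trial goes on to stage 2 (226 + 187, sections 9 and 11).
- I, the true proportion with a new complication by one year: not in the documents. Assumed 20%, with 10% and 30% as alternatives.
- b, the share of enrolled women already positive before surgery, after the lymphedema exclusion: not in the documents. Assumed range 0 to 10%.
- Prior positivity is taken to persist and to be independent of new complications. Every patient is taken to return the questionnaire.

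**Formula.** A woman counts as positive if she has a new complication, or if she has none but was positive already:

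apparent proportion = I + b(1 − I), so bias = b(1 − I).

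The bias is smaller than b, because an already-positive woman who also develops a new complication would have been counted anyway.

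**Standard errors at I = 20%.**
- N = 226: √(0.2 × 0.8 / 226) = 0.0266, or 2.7 points.
- N = 413: √(0.2 × 0.8 / 413) = 0.0197, or 2.0 points.

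**Results at I = 20%** (bias = 0.8 × b).

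| b | Apparent proportion | Bias (points) | Extra cases, N = 226 | Extra cases, N = 413 | Bias / SE, N = 226 | Bias / SE, N = 413 |
|---|---|---|---|---|---|---|
| 0 | 20.0% | 0 | 0 | 0 | 0 | 0 |
| 2% | 21.6% | 1.6 | 3.6 | 6.6 | 0.6 | 0.8 |
| 5% | 24.0% | 4.0 | 9.0 | 16.5 | 1.5 | 2.0 |
| 10% | 28.0% | 8.0 | 18.1 | 33.0 | 3.0 | 4.1 |

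**Other values of I.**
- I = 10%: b = 5% gives 14.5% and b = 10% gives 19.0% (bias 4.5 and 9.0 points).
- I = 30%: b = 5% gives 33.5% and b = 10% gives 37.0% (bias 3.5 and 7.0 points).

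**Threshold.** At I = 20%, the bias exceeds one standard error once b is above 0.0266 / 0.8 = 3.3% (N = 226) or 0.0197 / 0.8 = 2.5% (N = 413).

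**The case against.** Four arguments stand against the point.

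1. **The main pre-existing condition is already excluded.** Known lower limb lymphedema is an exclusion criterion, and a history and examination are done before surgery. The other complications that section 2 names, in its phrase "increased risk for lymphatic complications such as lymphedema, lymphocysts and in rare cases lymphatic ascites", are presented there as risks of lymphadenectomy. This stands, and it limits the point to undiagnosed or non-specific leg complaints. It does not remove the point: a woman without a lymphedema diagnosis can still score on swelling or heaviness, and an unspecified examination does not replace a baseline score.

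2. **The questionnaire cannot be seen.** It is called validated, and section 7 refers to forms in an appendix that is not in the text available. If its items ask about change since surgery, most of the bias disappears. This stands, and it is why the conclusion is that incidence may be overstated. A reader might infer that prior complaints will certainly be counted as new; the documents do not support that.

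3. **The plan is more than a single reading at one year.** A reader might infer that it yields only a one-year prevalence. That overlooks the symptom-triggered administration, which can help to place onset after surgery. It does not help for a woman whose complaints began earlier and who reports them afterwards.

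4. **The objective is minor.** It is listed last, and has no hypothesis, precision target, stopping rule or role in the sample size. Because all patients are planned for full lymphadenectomy, no comparison with sentinel node removal alone rests on it. This stands and bears on priority.

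**Conclusion.** The point holds in a limited form. The plan uses a questionnaire to define incidence, plans it only at symptoms and at one year after surgery, and provides neither a preoperative reading nor a rule for separating new from prior complaints. Incidence may be overstated by b(1 − I), unless the instrument itself asks about change since surgery.

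The size cannot be determined from the documents. It is nil if the exclusion removes every woman who would score positive, below one standard error at b = 2%, and about 1.5 to 4.1 standard errors for b between 5% and 10%. The top of that range applies only if the trial reaches 413 patients. These figures rest on the assumed I = 20%, on independence and on complete returns.

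A reader might take the whole baseline rate b as the bias. That is an upper bound, reached only as I approaches zero. A reader might also infer that the trial's main result is affected. It is not: sensitivity, the false negative rate and negative predictive value rest on nodal histology, and the sample size rests on node-positive patients. The change is worth making because it is cheap and a missed baseline cannot be recovered.

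**What to change.** - **Section 7:** add the same questionnaire at the preoperative visit.
- **Section 8:** name the instrument and the rule for a positive result. Define incidence as a new positive result at any postoperative administration up to and including one year, symptom-triggered or at one year, among women negative at baseline. Counting only the one-year score would lose complications that were recorded at symptoms and resolved earlier. Report change from baseline for all women, including those positive at baseline.
- **Patients already operated on without a baseline:** report one-year prevalence separately, and label it as such.
- **If the instrument already asks about change since surgery:** say so in section 8. That would largely answer the point.

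The cost is one self-completed form at a contact that already takes place, a small burden for patients, and a split report for those without a baseline. The loss of precision is slight: if b = 10%, 226 × 0.9 ≈ 203 women remain in the denominator, and at I = 20% the standard error goes from 2.7 to √(0.2 × 0.8 / 203) = 2.8 points.
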